### **11.3.5.2. Physical examination**

Abnormal findings in physical examinations will be recorded as adverse events or baseline medical history and will be included in the respective summaries.

### **11.3.5.3. Vital signs**

Vital signs measurements will be summarized by dose level using descriptive statistics.

### **11.3.5.4. ECG**

12-lead ECG results will be summarized by dose level.

### **11.3.5.5. Clinical laboratory tests**

Clinical laboratory test values outside the normal range will be flagged in the data listing. Laboratory data will be summarized by dose level using descriptive statistics. The results of the immune safety tests will be summarized appropriately. NCI CTCAE Version 4.0 Grade will be assigned to some of the laboratory parameters, which are included in CTCAE Version 4.0. Laboratory values will be listed. The laboratory values which are outside normal range will be flagged as H (above high normal limit), L (below lower normal limit), or A (abnormal) in the data listings. The NCI CTCAE Version 4.0 Grade will also be flagged in the data listings.

### **11.3.5.6. ECOG performance status**

ECOG performance status will be summarized by dose level using descriptive statistics.

### **11.3.6.Immunogenicity**

A listing will be provided of all available immunogenicity data. A listing of immunogenicity data from those subjects with at least one positive Human Anti-Human Antibody (HAHA) at any time point will be provided by dose regimen. The frequency of subjects with at least one positive HAHA assessment, frequency of subjects who develop HAHA after a negative baseline assessment will be provided by dose. To examine the potential relationship between immunogenicity and safety, the frequency and type of AEs of special interest may be examined by overall immunogenicity status.

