### **Treatment cycle and route of administration:**

Each cycle consists of 4 weekly intravenous infusions at the assigned dose level.

Patients with good tolerability and disease control will continue treatment until disease progression or up to the maximum of one year, withdrawal from study or death, whichever comes first. If the individual patient still benefits from the Investigational Product after one year of treatment, extending the treatment beyond one year may be arranged with the Sponsor.

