### **Immunogenicity studies**

---

 For patients with hepatocellular carcinoma, mRECIST is used to evaluate treatment effect[6]

[figure not shown]
Serum samples used to evaluate the presence of antibody against HLX06 will be obtained prior to every infusion of HLX06 in cycle 1 and before the first infusion in subsequent 5 cycles or up to 24 weeks, whichever comes first; at the end of therapy, and at the 28-day follow-up visit, whenever possible.

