### **8.2. Immunogenicity**

Immunogenicity refers to the development of an immune response to the HLX06 itself, and is characterized by the antibodies (ADA) that the patients may develop to react with HLX06. These may result in more rapid clearance of the IP from the bloodstream or predispose the patient to infusion reactions upon retreatment with IP at a later date. The ADA may also likely potentiate the drug effect by prolonging its half-life. Blood samples for immunogenicity analysis are mandatory and will be collected from all patients prior to every infusion of IP in Cycle 1 and before first infusion in subsequent 5 cycles or up to 18 weeks, whichever comes first and on the day of follow-up visit 1.

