## **10.2. Adverse event collection period**

All protocol-related serious adverse events must be collected from the signing of the study specific informed consent until study drug administration.

All serious and non-serious adverse events reported from the time of study drug administration until 28 days following last infusion of study drug administration will be collected, whether elicited or spontaneously reported by the patient.

Serious adverse events occurring after the study-specific informed consent is signed but prior to the first dose of the investigational product will be collected only if they are considered by the investigator to be causally related to the study required procedures.

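### The optional look at AEs by overall antibody status does not separate antibody from time on treatment, so it can show an AE difference when there is none (minor)

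*Combined protocol and SAP*

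**What the plan says.** Section 11.3.6 states a purpose, "To examine the potential relationship between immunogenicity and safety", and names one way of pursuing it: "the frequency and type of AEs of special interest may be examined by overall immunogenicity status". Overall status is not defined. The positivity category used beside it, for a listing, is "those subjects with at least one positive Human Anti-Human Antibody (HAHA) at any time point".

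Three other parts of the plan determine what that comparison would contain.

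- **Antibody sampling.** The Synopsis (Immunogenicity studies) takes samples "prior to every infusion of HLX06 in cycle 1 and before the first infusion in subsequent 5 cycles or up to 24 weeks", plus the end of therapy and the 28-day visit. Section 8.2 has "prior to every infusion of IP in Cycle 1 and before first infusion in subsequent 5 cycles or up to 18 weeks", plus follow-up visit 1, and the Section 14 footnote also says 18 weeks.
- **Time on treatment.** Patients are treated "until disease progression or up to the maximum of one year, withdrawal from study or death, whichever comes first".
- **AE collection.** Under Section 10.2, AEs "from the time of study drug administration until 28 days following last infusion of study drug administration will be collected". Section 11.3.5.1 summarises them as the number and proportion of patients with at least one event.

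No section gives an onset-order rule, a landmark, time-updated status or an exposure adjustment for this comparison. Section 11.3.2 summarises exposure by dose level only.

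**The concern.** A patient who stays on HLX06 longer is sampled more often and observed longer for AEs. If patients are sorted by whether they were ever positive, the positive group is enriched for long stayers, and long stayers accumulate AEs whether or not antibody matters. In addition, an infusion reaction at the first dose counts against an antibody first detected months later.

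Section 8.2 raises the possibility that antibody predisposes to infusion reactions on retreatment. That is a statement about order, antibody first and event second. A table by ever-positive status cannot address order, and in a first-in-human study it could be read as a safety signal, or as reassurance, that the data do not contain.

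**Working it through.** The plan gives no figure for this comparison, so there is none to reproduce. The check asks what the comparison shows when antibody and AEs are independent.

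**1. Exposure from the schedule.**
- Patient leaving after cycle 1: last infusion at week 3 (day 22), so AE collection ends at week 3 + 4 = 7. Samples: 4 in cycle 1 + 1 at follow-up visit 1 = 5.
- Patient completing cycle 6: cycle 6 starts at week 20 and its fourth infusion is at week 23, so collection ends at week 23 + 4 = 27. Samples: 4 + 5 + 1 = 10 under the 24-week limit, or 4 + 4 + 1 = 9 under the 18-week limit. The Synopsis end-of-therapy sample is not counted.
- Patient treated for a year: AE collection to about 52 + 4 = 56 weeks.

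**2. Hand illustration.** Assume half the patients leave after cycle 1 and half after cycle 6, an AE hazard of 0.03 per week and an antibody hazard of 0.02 per week, independent of each other. The probability of an event by week t is 1 − exp(−hazard × t).

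| | 7 weeks | 27 weeks |
|---|---|---|
| AE | 1 − e^(−0.21) = 0.189 | 1 − e^(−0.81) = 0.555 |
| Antibody | 1 − e^(−0.14) = 0.131 | 1 − e^(−0.54) = 0.417 |

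- AE proportion, ever-positive: (0.131 × 0.189 + 0.417 × 0.555) / (0.131 + 0.417) = 0.256 / 0.548 = 47%.
- AE proportion, never-positive: (0.869 × 0.189 + 0.583 × 0.555) / (0.869 + 0.583) = 0.488 / 1.452 = 34%.

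The gap is 13 points, although within each duration the true difference is 0.

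**3. Null simulation.** There were 24 settings of 400,000 patients each. Sampling was at weeks 1, 2, 3, 4, 8, 12 and 16 (and 20 under the 24-week limit) while on treatment, plus 28 days after treatment ended; AEs were counted to the same point. The following are assumptions, not document figures: exponential treatment time with median 8, 16 or 26 weeks, capped at 52; antibody hazard 0.005 or 0.02 per week; constant AE hazard 0.01 or 0.03 per week; AEs do not end treatment.

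- Ever-positive patients had more AEs in all 24 settings: risk ratio 1.27 to 1.61.
- Subtracting the rounded proportions, the gap is 7 to 10 points at AE hazard 0.01 and 12 to 19 points at 0.03. It is 10 or more in 16 of 24 settings.
- Example (median 16 weeks, 24-week limit, antibody 0.02, AE 0.03): 59% versus 40%, a gap of 19 points.
- Of first AEs in ever-positive patients, 60% to 74% came before the first positive sample (64% in the example). This share depends on the 28-day sample: in the one setting rerun without it, the share was 34%, with AEs in 27% versus 20%.

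**4. When AEs end treatment.** Same 24 settings, varying the share of on-treatment AEs that stop treatment:

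| Share stopping | Null risk ratio |
|---|---|
| 0% | 1.27-1.60 |
| 10% | 1.23-1.53 |
| 25% | 1.20-1.41 |
| 50% | 1.09-1.27 |
| 100% | 0.82-1.00 |

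The 0% row is a separate run of step 3, so its upper end differs by simulation error.

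**5. At trial size.** With 30 patients, median 16 weeks and AE hazard 0.01, positive patients show an AE excess of 20 points or more in 33% of trials (antibody hazard 0.005) or 27% (0.02). When everyone is treated for the same 16 weeks, chance alone gives 20% and 10%.

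**6. Candidate remedies under the same null.**
- Unstratified rate after versus before the first positive sample, constant hazard: ratio 0.97 to 1.04.
- The same ratio with the AE hazard concentrated early (assumed 0.06-0.10 per week in weeks 0-4, then 0.01-0.02): 0.34 to 0.69, a false protective effect, because later time is compared with earlier time.
- Time-updated status stratified by time since first dose, early-peaking hazard: 0.97 to 1.04.
- Landmark at week 4, constant hazard: 0.94 to 1.10.

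**The case against.** The strongest reply has three parts.

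**Little rests on it.** The text says AEs may be examined. No test, model or decision is attached, at most 30 patients are involved, and under Section 11.1.1 the MTD comes from first-cycle DLTs. The plan also lists all antibody data, lists AEs individually and records AE start and end dates (Sections 11.3.6, 11.3.5.1 and 10.1), so a careful reader could work out the order patient by patient. This stands, and it is why the point is minor. It does not remove the fault, because the one summary the plan names for this question is the one that mixes antibody with duration.

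**The direction is not fixed.** Section 7.2.5 makes an AE a possible reason to stop, and when every AE stops treatment the excess vanishes or reverses. For infusion reactions, Sections 6.4 and 7.2.2.2 provide for premedication after a reaction, so risk may fall with each infusion. Assuming a per-infusion risk of 10-15% that falls by a factor of 0.5-0.8 each time, the gap is only about 1 to 6 points. With the fastest decline and half of reactions stopping treatment, it reverses to about −7 to −14. This also stands. However, universal stopping is not what the plan describes: Section 6.4 manages many toxicities with treatment continuing, and Section 7.2.4.2 lets patients with reversible DLTs continue. A reversed gap would be misleading too, because it could hide a real signal.

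**A simple before/after rate ratio is not a cure.** Step 6 confirms this, and the fix below allows for it.

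A reader might also infer that the plan commits to this comparison, that it defines overall status as ever-positive, or that a false-positive test result is likely. The documents support none of these. The comparison is optional, ever-positive is an inference from neighbouring sentences, and no test is named.

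**Conclusion.** The point holds as a minor one. If Section 11.3.6 is carried out on its most natural reading, the comparison can show an AE difference where none exists, and nothing in the plan guards against this. With constant hazards and AEs that do not end treatment, the false excess is roughly 10 to 20 points in most settings, and most first AEs in positive patients precede the first positive sample.

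Those figures rest on assumed treatment durations and hazards that the documents do not give, and the share preceding positivity rests partly on the 28-day sample being taken. It would go too far to say that a spurious excess will appear, or that the bias always points towards harm: the size depends on when AEs occur and the sign on how often they end treatment. The MTD and the primary safety tabulations are unaffected.

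**What to change.** In Section 11.3.6:

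1. Define antibody status by the date of the first positive sample, and state which events count as AEs of special interest, since the documents do not define them.
2. List each AE of special interest by onset before or after that date. Patients positive at baseline are shown separately; patients never positive contribute only before-positivity time.
3. If rates are compared, use time-updated status stratified by time since first dose, or a landmark such as the end of cycle 1. Do not use a crude before/after rate ratio.
4. Reconcile the antibody sampling limit, which is 24 weeks in the Synopsis and 18 weeks in Section 8.2 and the Section 14 footnote, because it affects who can be found positive and when.

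The cost is a few sentences and a little programming; the necessary dates and samples are already collected. The drawback is that at most 30 patients will yield few events after a first positive sample, so any ratio will be imprecise and the timing listing is the main output. A landmark also ignores antibody first detected after it.

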### **11.3.7.Pharmacokinetic analysis**

The pharmacokinetic parameters will be calculated and listed for each patient and treatment cycle, alone with summary statistics including arithmetic and geometric means; standard

deviation; minimum, maximum, and median values; and coefficients of variations. The PK data will also be displayed graphically, as appropriate. Exploratory analyses on the PK data and their relationship to PD, safety, and immunogenicity evaluation may be investigated. Pharmacokinetic concentrations from limited samples will be listed, and may be used in combination with other studies for exposure-response or population pharmacokinetic modeling.

#### **11.3.8. Pharmacodynamic analysis**

The PD data will be assessed descriptively whenever possible and by exploratory statistical the relationship between PK and PD will be explored and the strength of the relationship will be assessed, whenever possible, comparisons of both raw and relative-to-baseline data.

## **12. ETHICAL ASPECTS**

### **12.1. Ethics and good clinical practice**

This study must be carried out in compliance with the protocol and the requirement of Clinical Practice (GCP), as described in International Conference on Harmonization (ICH) Harmonized Tripartite Guidelines (ICH E6R1 and its addendum) or similar regulations published by local regulatory agencies (e.g. the GCP guidance published by Taiwan Food and Drug Administration or Chinese Food and Drug Administration, US Code of Federal Regulations, Title 21, Part 50[21CFR50], and Title 21, Part 312[21CFR312]).

The protocol and any amendments and the patient informed consent will receive Institutional Review Board/Independent Ethics Committee (IRB/IEC) approval/favorable opinion before initiation of the study. Study personnel involved in conducting this study will be qualified by education, training, and experience to perform their respective tasks.

This study will not use the services of study personnel where sanctions have been invoked or where there has been scientific misconduct or fraud (e.g., loss of medical license, debarment). All potential serious breaches must be reported to the Sponsor immediately. A serious breach is a breach of the conditions and principles of GCP in connection with the study or the protocol, which is likely to affect, to a significant degree, the safety or physical or mental integrity of the patients of the study or the scientific value of the study.

### **12.2. Confidentiality of study patients**

Investigators must assure that the privacy of patients, including their personal identity and all personal medical information, will be protected at all times, as required by law. In CRFs and other study documents submitted to the Sponsor or its designee, patients will be identified by their initials, patient number, date of birth, and gender.

Personal medical information may be reviewed and/or copied for research, quality assurance, and/or data analysis. This review may be conducted by the study monitor, properly authorized persons on behalf of the Sponsor, an independent auditor, IRBs/IECs or regulatory authorities. Personal medical information will always be treated as confidential.

### **12.3. Institutional review board (IRB)/independent ethics committee (IEC)**

Before implementing this study, the protocol, the proposed ICF, and other information provided to patients must be reviewed by an IRB/IEC. A signed and dated statement that the protocol,

and ICF, patient recruitment materials/process (eg, recruitment advertisements), and any other written information to be provided to patients have been approved by the IRB/IEC must be given to the Sponsor or its designee before study initiation. The name of the chairperson of the IRB/IEC (preferred) or the IRB's Health and Human Safety Assurance number must be supplied to or its designee along with the IRB approval. Any amendments to the protocol which need formal approval, as required by local law or procedure, will be approved by this committee. The IRB/IEC will also be notified of all other administrative amendments (i.e., administrative changes).

The Investigator or Sponsor or its designee should also provide the IRB/IEC with a copy of the Investigator Brochure or product labeling, information to be provided to patients and any updates.

The investigator or sponsor should provide the IRB/IEC with reports, updates and other information (eg, expedited safety reports, amendments and administrative letters) according to regulatory requirements or institution procedures.

#### **12.4. Informed consent**

Investigators must ensure that patients, or, in those situations where consent cannot be given by patients, their legally acceptable representatives, are clearly and fully informed about the purpose, potential risks/benefits, and other critical issues regarding clinical studies in which they volunteer to participate.

The Investigators, or their designees, will explain to each patient (or legally authorized representative) the nature of the research study, its purpose, the procedures involved, the expected duration of patient participation, alternative treatment options, potential risks and benefits involved, and any discomfort which may occur during the patient's participation in the study. Each patient will be informed that participation in the study is voluntary and that he/she may withdraw from the study at any time and that withdrawal of consent will not affect his/her subsequent medical care or relationship with the treating physician and caring medical team.

The ICF must be submitted by the Investigator with the protocol for IRB/IEC approval. The Sponsor or its designee supplies a proposed ICF template that complies with regulatory requirements, includes all elements required by ICH, GCP and applicable local regulatory requirements, and is considered appropriate for the study. The sample informed consent form will adhere to the ethical principles that have their origin in the Declaration of Helsinki. Any changes to the proposed ICF suggested by the Investigator must be agreed to by the Sponsor or

its designee before submission to the IRB/IEC, and a copy of the approved version must be provided to the Study Monitor or its designee after IRB/IEC approval.

Investigator must:

Provide a copy of the consent form and written information about the study in the language in which the patient is most proficient prior to clinical study participation. The language must be non-technical and easily understood.

Allow time necessary for patient or patient's legally acceptable representative to inquire about the details of the study.

Obtain an informed consent signed and personally dated by the patient or the patient's legally acceptable representative and by the person who conducted the informed consent discussion.

Obtain the IRB/IEC's written approval/favorable opinion of the written informed consent form and any other information to be provided to the patients, prior to the beginning of the study, and after any revisions are completed for new information.

If informed consent is initially given by a patient's legally acceptable representative or legal guardian, and the patient subsequently becomes capable of making and communicating their informed consent during the study, then consent must additionally be obtained from the patient.

Revise the informed consent whenever important new information becomes available that is relevant to the patient's consent. The investigator, or a person designated by the Investigator, should fully inform the patient or the patient's legally acceptable representative or legal guardian, of all pertinent aspects of the study and of any new information relevant to the patient's willingness to continue participation in the study. This communication should be documented.

The consent form must also include a statement that the regulatory authorities have direct access to patient records.

Patients who meet the eligibility criteria but are unable to give their written consent (e.g., stroke patients) may only be enrolled in the study with the consent of a legally acceptable representative. The patient must also be informed about the nature of the study to the extent compatible with the patients' understanding, and should they become capable, personally sign and date the consent form as soon as possible.

The rights, safety, and well-being of the study patients are the most important considerations and should prevail over interests of science and society.

## **13. ADMINISTRATIVE REQUIREMENTS**

### **13.1. Protocol amendments**

Any change or modification to this protocol requires a written protocol amendment that must be approved by the Sponsor before implementation. Amendments significantly affecting the safety of patients, the scope of the investigation, or the scientific quality of the study require additional approval by the IRB/IEC of all centers and, by the local regulatory authority. A copy of the written approval of the IRB/IEC must be given to the study monitor, or their designee. Examples of amendments requiring such approval are:

Increase in drug dosage or duration of exposure of patients, or any significant increase in the number of patients under study;

Significant change in the study design (e.g., addition or deletion of a control group, or rule of dose escalation or de-escalation);

Increase in the number of procedures to which patients are exposed; or

Addition or deletion of a test procedure intended to improve safety monitoring.

These requirements for approval should in no way prevent any immediate action from being taken by the Investigator or by the Sponsor in the interests of preserving the safety of all patients in the study. If an immediate change to the protocol is deemed by the Investigator to be necessary and is implemented by him/her for safety reasons, the Sponsor should be notified and the IRB/IEC for the study site should be informed within 1 working day. Any significant deviation must be documented in the CRF.

If a deviation or change to a protocol is implemented to eliminate an immediate hazard(s) prior to obtaining IRB/IEC approval/favorable opinion, as soon as possible the deviation or change will be submitted to: (1) IRB/IEC for review and approval/favorable opinion; (2) the Sponsor and (3) regulatory Authority(ies), if required by local regulations.

If an amendment substantially alters the study design or increases the potential risk to the patient: (1) the consent form must be revised and submitted to the IRB(s)/IEC(s) for review and approval/favorable opinion; (2) the revised form must be used to obtain consent from patients currently enrolled in the study if they are affected by the amendment; and (3) the new form must be used to obtain consent from new patients prior to enrollment.

Amendments affecting only administrative aspects of the study do not require formal protocol amendments or IRB/IEC approval; however, the IRB/IEC for each center must be kept informed of such administrative changes. Examples of administrative changes not requiring

formal protocol amendments and IRB/IEC approval that can be treated as administrative amendments include, but are not limited to: (1) changes in the staff used to monitor studies; (2) minor changes in the packaging or labeling of study drug.

